5	34	72	45
6	38	86	52
7	42	100	58
8	45		65
9	48		72
10	52		79
11	56		88
12	60		100
13	65		
14	71		
15	78		
16	87		
17	100		

^aThe maximum score for the chest symptoms domain is 12. The maximum score for the Cough & Sputum domain is 7.

Table 4: SAS Coding Instructions for Computing Daily Scores

The following example assumes all original item responses are coded as 0, 1, 2, 3, 4, etc. on the data collection forms or electronic data capture system, ordered from least severe to most severe. In this case, only items 3, 8, 9, 10, 11, and 14 need to be recoded to form item-level scores. If the original codes begin with 1 for least severe (e.g., 1, 2, 3, 4, 5 for question 1), then the codes must be shifted to a 0 starting point for all items before these SAS statements can be used.

1. Assign raw score values associated with each response category for the EXACT® items:
	<pre> if q3 in (1,2) then q3=1; else if q3 in (3) then q3=2; else if q3 in (4) then q3=3; if q8 in (3,4) then q8=3; if q9 in (3,4) then q9=3; else if q9 in (5) then q9=4; if q10 in (3,4,5) then q10=3; if q11 in (3,4,5) then q11=3; if q14 in (3,4) then q14=3; rawsum=sum (of q1-q14); breathlesssum=sum (of q7-q11); coughsum=sum (of q2 q3); chestsum=sum (of q1 q5 q8); </pre>

2. Assign the EXACT® Total score for each raw summed score:
	<pre> select (rawsum); when(0) Exact_total=0; when(1) Exact_total=8; when(2) Exact_total=13; when(3) Exact_total=17; when(4) Exact_total=20; when(5) Exact_total=23; when(6) Exact_total=25; when(7) Exact_total=27; when(8) Exact_total=28; when(9) Exact_total=30; when(10) Exact_total=31; when(11) Exact_total=33; when(12) Exact_total=34; when(13) Exact_total=36; when(14) Exact_total=37; when(15) Exact_total=38; when(16) Exact_total=39; when(17) Exact_total=40; when(18) Exact_total=41; when(19) Exact_total=42; when(20) Exact_total=43; when(21) Exact_total=44; when(22) Exact_total=46; when(23) Exact_total=47; when(24) Exact_total=48; when(25) Exact_total=49; when(26) Exact_total=50; when(27) Exact_total=51; when(28) Exact_total=52; </pre>

	<pre> when(29) Exact_total=53; when(30) Exact_total=54; when(31) Exact_total=55; when(32) Exact_total=57; when(33) Exact_total=58; when(34) Exact_total=59; when(35) Exact_total=60; when(36) Exact_total=61; when(37) Exact_total=63; when(38) Exact_total=64; when(39) Exact_total=65; when(40) Exact_total=67; when(41) Exact_total=68; when(42) Exact_total=70; when(43) Exact_total=72; when(44) Exact_total=73; when(45) Exact_total=75; when(46) Exact_total=77; when(47) Exact_total=80; when(48) Exact_total=83; when(49) Exact_total=87; when(50) Exact_total=92; when(51) Exact_total=100; otherwise;</pre>

3. Assign the Breathlessness domain score for each domain raw summed score:
	<pre> select (breathlessnessum); when(0) Breathlessness=0; when(1) Breathlessness=11; when(2) Breathlessness=19; when(3) Breathlessness=25; when(4) Breathlessness=30; when(5) Breathlessness=34; when(6) Breathlessness=38; when(7) Breathlessness=42; when(8) Breathlessness=45; when(9) Breathlessness=48; when(10) Breathlessness=52; when(11) Breathlessness=56; when(12) Breathlessness=60; when(13) Breathlessness=65; when(14) Breathlessness=71; when(15) Breathlessness=78; when(16) Breathlessness=87; when(17) Breathlessness=100;</pre>

4. Assign the Cough & Sputum domain score for each domain raw summed score:
	<pre> select (coughsputum); when(0) Coughsputum=0; when(1) Coughsputum=13; when(2) Coughsputum=25; when(3) Coughsputum=39; when(4) Coughsputum=56; when(5) Coughsputum=72; when(6) Coughsputum=86; when(7) Coughsputum=100;</pre>

5. Assign the Chest Symptom domain score for each domain raw summed score:

```
select (chestsum);  
when(0) Chestsymptom=0;  
when(1) Chestsymptom=12;  
when(2) Chestsymptom=23;  
when(3) Chestsymptom=31;  
when(4) Chestsymptom=38;  
when(5) Chestsymptom=45;  
when(6) Chestsymptom=52;  
when(7) Chestsymptom=58;  
when(8) Chestsymptom=65;  
when(9) Chestsymptom=72;  
when(10) Chestsymptom=79;  
when(11) Chestsymptom=88;  
when(12) Chestsymptom=100;
```

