7.1.4.7 Questionnaire EXACT-PRO

The EXACT is a 14-item patient reported outcome (PRO) daily diary used to quantify and measure exacerbations of COPD (Mackay 2014⁴). This instrument provides a single, standardised approach for assessing the symptomatic manifestations of COPD exacerbations, with a development and validation history consistent with guidelines proposed by the FDA, EMA and well-known measurement principles.

The questionnaire is composed of 14 items covering various domains such as breathlessness, cough and sputum, chest symptoms, and overall status (tiredness, weakness, sleep disturbances). Each question is individually weighted to provide a total score varying from 0 to 100. The health status of the subject is correlated to the global score, meaning a higher score corresponds to a more severe health status of the subject.

The EXACT-PRO will be completed once a day in the evening by the subject. The EXACT score will be monitored and will raise an alert to the investigator in case of relevant increases.

EXACT Total Score

An EXACT Total score is computed for each day of diary collection. The EXACT Total score is based on a logit scoring system with conversion to a 0 to 100 scale for ease of interpretation and use. The total score is used in the determination of exacerbation frequency, severity and duration of exacerbation. Specifically, changes in the total score are used to define onset and recovery from an exacerbation event and the magnitude of that event.

EXACT Domain Scores

Additional information regarding the patient's condition can be obtained through 3 domain scores embedded within the EXACT measure: Breathlessness, Cough & Sputum, and Chest Symptoms. These scores also range from 0 to 100 with higher scores indicating more severe symptoms.

Appendix C describes the EXACT raw scores and EXACT scoring instructions to compute the EXACT daily scores and event frequency, duration and severity.

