If the EXACT Total score is 0, change it to missing. This scoring rule is based on previous validation work demonstrating that moderate-to-severe COPD patients will experience symptom(s) each day, and a score of zero on all 14 EXACT items is likely to represent a situation where in order to complete the diary quickly, the respondent did not accurately report their daily symptom(s).

Where no diary entry exists for a given day, create a record in the data file for that day and enter a missing value for the EXACT Total score. Each day a patient is followed in the study must have a record for the day, even if there is no data and the EXACT Total score is missing.

Domain Scores

Three respiratory symptom domains are also embedded within the EXACT measure: Breathlessness, Cough & Sputum, and Chest Symptoms.

To compute domain scores:

Item assignments to domains are as follows. Please note that items 4, 12, 13, and 14 do not correspond to a domain score and are not used in domain-specific analyses.

- Breathlessness – Items 7, 8, 9, 10, and 11
- Cough & Sputum – Items 2 and 3
- Chest Symptoms – Items 1, 5, and 6.

For each day, sum the item-level raw scores of the items comprising the domain to form the domain raw summed score. If no diary entry exists for a given day, leave the domain raw summed score missing.

Each domain raw summed score has its corresponding “EXACT Domain” score. For each domain raw summed score, look up the corresponding EXACT domain score from [Table 3](#) below. If no diary entry exists for a given day, leave the EXACT domain score missing.

If the daily EXACT domain score is 0, change it to missing. This scoring rule is based on previous validation work demonstrating that moderate to severe COPD patients will experience symptom(s) each day, and a score of zero on all 14 EXACT items is likely to represent a situation where in order to complete the diary quickly, the respondent did not accurately report their daily symptom(s).

2. Computing Event Frequency, Duration, and Severity

All exacerbation parameters are based on the EXACT Total score.

Baseline EXACT Total Score

For studies enrolling patients during a stable baseline period, baseline EXACT values are computed and used to identify the onset of EXACT events.

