A 3-day Rolling Average is used to account for day-to-day variability in EXACT scores. This is operationalized as a 3-day Rolling of the mean EXACT score [Day_{x-1}, Day_x, Day_{x+1}] initiated on Study Day 1 (Onset) and ends on Day 1 of recovery.

The 3-day Rolling Average will be calculated from Study Day 1 to Day 1 of recovery:

- At Day 1, the Rolling Average will be the total score of Study Day 1 (Onset), and will be missing if the total score of Study Day 1 is missing
- At Day 2 the Rolling Average will be the total score of Study Day 2, and will be missing if the total score of Study Day 2 is missing
- The Rolling Average at any other Day x (including Day 1 of recovery) will be computed as the mean of Study Day_{x-1}, Day_x, Day_{x+1}, if at least one of Day_{x-1}, Day_x, Day_{x+1} is available.

Only 1 of the 3 data points needs to be present for this computation.

Improvement from Day 1 in EXACT-PRO Rolling Average will be calculated as:

Improvement from Day 1 = Rolling Average at Day 1 - Rolling Average at Day x

The improvement from Day 1 in EXACT-PRO Rolling Average will be left missing if the Rolling Average at Day 1 cannot be computed or if it is missing at Day x.

Maximum Observed Value between Day 1 and Day 14

The Maximum Observed Value (MOV) is the highest Rolling Average EXACT score observed in the context of an EXACT exacerbation within the first 14 days of the exacerbation (i.e. between Day 1 and Day 14). The MOV is allowed to increase over the first 14 days of an exacerbation. Starting on Day 15 of an exacerbation, the MOV stays at the level on the 14th day for the remainder of the exacerbation.

Threshold for Improvement

Improvement is defined as a decrease in the Rolling Average EXACT score ≥ 9 points from the previous day's MOV during an event.

Recovery

Recovery is defined as the first day in which a patient experiences a persistent, sustained improvement in their condition over the observed period. Improvement must be present for 7 consecutive days. The first day of the 7-day period is designated as the first day of Recovery (Day_R).

Based on the scoring algorithm for Recovery, EXACT exacerbations can be categorized as Recovered, Censored, or Persistent Worsening. Recovered is defined as an EXACT exacerbation meeting the Recovery definition outline above. Censored is defined as an EXACT exacerbation that began within 28 days of study termination and did not meet the Recovery definition during that

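### SAP Appendix C turns every EXACT domain score of 0 into missing, so the domain analyses cannot record complete resolution of a symptom domain

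*SAP*

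**What the plan says.** Appendix C of the SAP contains two zero rules. For the Total score: "If the EXACT Total score is 0, change it to missing". For each domain: "If the daily EXACT domain score is 0, change it to missing". Neither carries a further condition. The same reason is given for both, namely that "a score of zero on all 14 EXACT items is likely to represent a situation where in order to complete the diary quickly".

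The domains are small. One is defined as "Cough & Sputum – Items 2 and 3"; Chest Symptoms has three items and Breathlessness five. Four of the 14 items belong to no domain.

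Daily scores then enter a 3-day rolling average, for which "Only 1 of the 3 data points needs to be present for this computation". Domain rolling averages feed the summaries and MMRMs in 8.6.3.7 and the AUCs in 8.6.3.9. Section 8.6.3.10 summarises domain scores descriptively up to Week 26. Change in the domain scores is part of secondary endpoint 12 (SAP 4.2).

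**The concern.** The reason covers a diary with nothing reported anywhere. The rule reaches further: it also removes a zero on one domain when the patient reported other symptoms that day and the Total score is accepted as valid. Such days are to be expected, because the exacerbation definition (SAP 7.1.4.1) joins dyspnoea, cough and sputum with and/or, and the trial follows patients through recovery.

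Zero is the best possible domain value, so whether a value goes missing depends on the value itself. The SAP relies on missing at random in 7.2.1, stated there for the primary-endpoint MMRM. The domain rule does not meet that condition. At stake is whether the domain analyses can show a benefit that takes the form of a symptom disappearing.

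**Working it through.** The plan gives no figure for this point, so there is none to reproduce. The steps below apply the SAP's own scoring rules. All daily scores and zero frequencies are assumed, because the documents give none.

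**1. Can a domain be 0 on a valid day?** The maximum raw sum is 51 (Appendix C, Table 2). The domain maxima are 7 (Cough & Sputum), 12 (Chest Symptoms) and 17 (Breathlessness) (Table 3). With one domain at 0, the remaining items can reach:
- Cough & Sputum at 0: 51 − 7 = 44, Total score 73
- Chest Symptoms at 0: 51 − 12 = 39, Total score 65
- Breathlessness at 0: 51 − 17 = 34, Total score 59

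So the Total score is kept while the domain zero is removed.

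**2. Observable floor.** The lowest non-zero values in Table 3 are 11 (Breathlessness), 12 (Chest Symptoms) and 13 (Cough & Sputum).

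**3. Isolated zero days.**
- Days 0, 13, 0: (0 + 13 + 0)/3 = 4.3 with zeros kept; 13/1 = 13.0 under the rule.
- Days 13, 0, 13: 26/3 = 8.7 with zeros kept; 26/2 = 13.0 under the rule.

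**4. Sustained resolution.** Assumed Cough & Sputum scores: 86, 56, 39, 25, 13, then 0 from Day 6.

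| Rolling average | Zeros kept | Rule |
|---|---|---|
| Day 3 | 40.0 | 40.0 |
| Day 5 | (25 + 13 + 0)/3 = 12.7 | (25 + 13)/2 = 19.0 |
| Day 6 | 13/3 = 4.3 | 13.0 |
| Days 7, 10, 14, 29 | 0 | missing |

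Under the rule 6 of 14 rolling averages remain to Day 14. That is 43%, below the 50% limit in SAP 7.1.4.9, so the Day 1–14 AUC is missing. The Day 1–10 AUC survives (6 of 10) and is 21.1 against 20.2 with zeros kept, dividing by b − a = 9. Trailing gaps are not bridged, because 7.1.4.9 skips over only values lying between two observed ones.

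If the course is 86, 72, 56, 39, 25, 13, then 0 from Day 7, then 7 of 14 values remain (50%) and the Day 1–14 AUC is computed: 20.1 against 19.5. The effect on a surviving AUC is therefore small in these examples. The larger effect is loss of the AUC and of the later visits.

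**5. Baselines.** The stabilisation baseline needs at least 4 of Days 15–21 (SAP 8.1.5). Domain zeros on 4 of those days leave 3, so there is no baseline and no later change from it for that patient. A domain zero on Day 1 removes the acute baseline. The domain AUC is then missing (7.1.4.9), and the patient leaves the domain MMRM for want of a covariate (Appendix F, step 1).

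**6. Treatment difference in observed means.** Let p be the proportion with a domain zero and m the mean of non-zero scores, with subscript 0 for the comparator and 1 for the better arm.
- True difference = (1 − p0)·m0 − (1 − p1)·m1
- Under the rule = m0 − m1
- Hidden part = p1·m1 − p0·m0

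With p0 = 10%, p1 = 30% and m0 = m1 = 25: true 22.5 − 17.5 = 5.0; under the rule 25 − 25 = 0. With p1 = 20%: true 22.5 − 20.0 = 2.5; under the rule 0.

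If the non-zero means also differ, say 25 and 19 (two Breathlessness values in Table 3), with 10% and 30%: true 22.5 − 13.3 = 9.2; under the rule 6.0. Here 3.2 points are hidden, not the whole effect. The difference is attenuated whenever p1·m1 exceeds p0·m0.

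**The case against.** **The instrument may prescribe the rule.** The SAP cites the EXACT user manual, says openly where it departs from it (8.1.5, Appendix C), declares no departure here, and refers to earlier validation work. This stands as a limit, since the manual cannot be checked from these documents. It does not make the printed reason fit a single-domain zero.

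**The SAP is not plainly contradicting itself elsewhere.** Section 7.1.4.7 says of the domains that "These scores also range from 0 to 100 with higher scores indicating more severe symptoms", and Table 4 has "when(0) Coughsputum=0". The Total score has the same 0–100 range and the same kind of look-up line, and it too is set to missing at 0 in the text. These places do not show that domain zeros were meant to be kept. Table 4 simply has no set-to-missing step for any score.

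**The reach is limited.** Domain scores are parts of secondary endpoints, 8.6.3.10 has no model or test, and the protocol (13.5.1) treats all analyses as exploratory. This stands.

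**A reader might infer that the domain analyses cannot show recovery at all, or that any treatment difference vanishes.** Neither follows. Domain scores can still fall, for example from 86 to 13. Improvement and recovery are defined on the Total score only. The zero difference in step 6 arises only for observed means with identical non-zero scores in both arms; an MMRM also uses each patient's earlier values and need not give that result.

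**Conclusion.** The concern holds in a limited form. The rule removes valid zeros on days with a non-zero Total score, for a reason that applies only when all 14 items are 0. The domain summaries, MMRMs and AUCs cannot record complete resolution of a domain and are biased toward residual symptoms.

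The mechanism follows from the SAP text. Its size is unknown because the documents do not say how often domain zeros occur. Attenuation of the domain treatment difference is conditional on the arms differing in complete resolution; step 6 shows the range from partial to, in the extreme case, total. Total-score improvement and recovery and the primary FEV1 endpoint do not depend on this rule. It should be corrected, but it does not threaten the trial's main conclusion.

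**What to change.** Reword the domain rule so that domain scores are set to missing only on days when all 14 items are 0 (Total score 0) or no valid diary entry exists; otherwise a domain score of 0 is kept. Add the matching set-to-missing step for the Total and the three domains to the Table 4 code, which now has none. Report the number and percentage of domain zeros by arm.

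The cost is one sentence, a few lines of code and one table, with no new data. The downside is a possible departure from the instrument manual. If the manual prescribes the domain rule, list the change as a departure and keep the manual's scoring as a sensitivity analysis.

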8.6.3.7 Time to improvement based on EXACT-PRO total score

All EXACT-PRO rolling average results available at Day 3, 5, 7, 10, 14 and 29 will be summarised at each visit by treatment regimen using descriptive statistics. The improvements (changes) in EXACT-PRO rolling average from baseline (Day 1 pre-dose) will also be summarised at Day 3, 5, 7, 10, 14 and 29 by treatment regimen.

MMRM analysis using an unstructured covariance matrix and the Kenward-Roger adjustment for the denominator degrees of freedom will be performed for statistical comparison of treatment regimens with improvement in EXACT-PRO rolling average as an outcome. Model will consider treatment, severity of airflow limitation at baseline, blood eosinophils (%) value at baseline, time from start of current COPD exacerbation to first IMP dosing, presence of cardiovascular comorbidities at screening and COPD exacerbation treatment at screening as fixed effects and baseline EXACT-PRO Rolling Average score as covariate. In addition the baseline score-by-visit and the treatment-by-visit interactions will be included in the model.

LSMEAN and standard error (SE) of each treatment regimen, difference of LSMEANS between treatment regimens and their associated two-sided 95% CIs and corresponding two-sided P-values for Day 3, Day 5, Day 7, Day 10, Day 14 and Day 29 will be estimated by the model. P-values of the effects will also be presented.

The unstructured covariance matrix (which does not presume a particular correlation structure for repeated measurements within patients over time) will be used to adjust for the within-patient error variance covariance. In case model fails to converge, other covariance matrix structures will be considered in the sequence of Ante-dependence, Toeplitz, Heterogeneous AR(1), Heterogeneous Compound Symmetry, and Compound Symmetry.

Similar descriptive analysis and MMRM analysis as above will be performed for each of the 3 EXACT-PRO subscores.

The following figure will be produced for the EXACT-PRO total score and each of the 3 EXACT-PRO subscores:

- Mean EXACT-PRO Rolling Average over time for Day 1 to Day 29 by treatment regimen

Improvement based on EXACT-PRO total score is defined as a decrease in the Rolling Average EXACT score ≥ 9 points from the previous day's Maximum Observed Value during an event.

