8.6.3.9 Standardised AUC of EXACT-PRO over time

The standardised AUCs of EXACT-PRO (Day 1 to Day 3, Day 1 to Day 5, Day 1 to Day 7, Day 1 to Day 10, Day 1 to Day 14, Day 1 to Day 29) will be derived and summarised with standard descriptive statistics by treatment regimen.

The standardised AUC from Day 1 to Day 14 will be analysed using an ANCOVA model estimating the effect up to Day 14, using OC, including treatment, severity of airflow limitation at baseline, blood eosinophils (%) value at baseline, time from start of current COPD exacerbation to

first IMP dosing, presence of cardiovascular comorbidities at screening and COPD exacerbation treatment at screening as fixed effects and baseline EXACT-PRO Rolling Average score as a covariate.

The ANCOVA model results will be presented with LSMEAN and standard error (SE) of each treatment regimen as well as the adjusted mean difference between treatment regimens at Day 14 and associated two-sided 95% CIs. Each pairwise treatment regimen comparison will be tested at an alpha level of 5%. P-values of the effects will also be presented.

A similar ANCOVA model will be used to analyse the standardised AUC of EXACT-PRO from Day 1 to Day 7 and from Day 1 to Day 10.

All the analyses above will be repeated for each of the 3 EXACT-PRO subscores AUCs.

8.6.3.10 Change from Baseline at each inter-visit period and over the entire period of the study in the average EXACT-PRO total score and domain scores

All EXACT-PRO rolling average scores available will be summarised at baseline (Day 1 pre-dose) and at specific timepoints during the Acute Exacerbation Phase (Day 3, Day 5, Day 7, Day 10, Day 14) by treatment regimen using descriptive statistics. The improvements (changes) in EXACT-PRO rolling average score from baseline (Day 1 pre-dose) will also be summarised at these timepoints by treatment regimen (See SAP Section 8.6.3.7). Considering Stabilisation Phase, All EXACT-PRO rolling average scores available will be summarised at baseline (Stabilisation Phase), Day 29 (end of Week 4), Day 57 (end of Week 8), Day 85 (end of Week 12), Day 113 (end of Week 16), Day 141 (end of Week 20), Day 169 (end of Week 24) and Week 26 Visit during the Stabilisation Phase by treatment regimen using descriptive statistics. The changes in EXACT-PRO rolling average score from baseline (Stabilisation Phase) will also be summarised at these timepoints by treatment regimen.

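### SAP Appendix C stops the EXACT rolling average on the day of recovery, but the recovery definition and the fixed-day EXACT analyses to Day 14, Day 29 and Week 26 need later values

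*SAP*

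**What the plan says.** Appendix C gives the stop rule twice. The rolling average is "initiated on Study Day 1 (Onset) and ends on Day 1 of recovery", and then: "The 3-day Rolling Average will be calculated from Study Day 1 to Day 1 of recovery". It defines improvement as a fall of at least 9 points in this average from the previous day's maximum observed value. For recovery, "Improvement must be present for 7 consecutive days", and Day R is the first of the seven days. Sparse diaries are allowed for: "Only 1 of the 3 data points needs to be present for this computation".

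Other sections use the average on fixed days, with no restriction to patients who have not yet recovered:

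- SAP 8.6.3.7 fits an MMRM, with "corresponding two-sided P-values for Day 3, Day 5, Day 7, Day 10, Day 14 and Day 29 will be estimated by the model". It also plots "Mean EXACT-PRO Rolling Average over time for Day 1 to Day 29 by treatment regimen".
- SAP 8.6.3.9 derives AUCs from Day 1 to Days 3, 5, 7, 10, 14 and 29. Day 1–14 is tested by ANCOVA, and "A similar ANCOVA model will be used to analyse the standardised AUC of EXACT-PRO" to Days 7 and 10.
- SAP 7.1.4.9 sets the AUCs to Days 3–14 to missing when fewer than half the values exist. It replaces a missing closing value by the mean of the day before and the day after (Days 13 and 15 for Day 14).
- SAP 8.6.3.10 summarises the average as far as "Day 169 (end of Week 24) and Week 26 Visit during the Stabilisation Phase".

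**The concern.** The stop rule conflicts with the recovery definition in the same appendix and with every fixed-day analysis that falls after a patient's recovery. No passage extends the calculation past Day R.

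If the stop is applied, the lost values belong to patients who got better, and more of them would be on an effective drug. The deletion is triggered by Days R+1 to R+6, which are themselves deleted, so the missingness depends on unobserved data. SAP 7.2.1 declines to impute on the ground that MMRM is valid under missing at random. It says this for the primary endpoint and for drop-outs, and that ground would not hold here.

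At stake are the EXACT MMRM reported under secondary endpoint 7, the EXACT AUC (endpoint 8) and EXACT change over time (endpoint 12).

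**Working it through.** The plan states no figure that depends on this rule, so there is none to reproduce. The check has three parts.

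**1. Which AUCs are lost (SAP rules only).** With values ending on Day R, R values exist in a window of b days. The AUC is missing if R < b/2. If b/2 ≤ R < b, the 50% rule is met but the closing value is absent, and so is the day b+1 value needed to replace it.

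| Window | b/2 | AUC missing | Closing value and substitute absent |
|---|---|---|---|
| Day 1–7 | 3.5 | R ≤ 3 | R = 4–6 |
| Day 1–10 | 5 | R ≤ 4 | R = 5–9 |
| Day 1–14 | 7 | R ≤ 6 | R = 7–13 |

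**2. Single paths (assumed scores, Appendix C rules).**

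- Score 52 falling 1.5 a day to 38. On Day 7 it is 52 − 6 × 1.5 = 43, which is 9 below the maximum, so R = 7. The Day 1–14 AUC on all days is 43.1. The area over Days 1–7 is 6 × (52 + 43)/2 = 285. Cut at Day R, the AUC is 285/13 = 21.9 with the printed divisor or 285/6 = 47.5 over the observed span. The two cut versions err in opposite directions.
- Score 52 falling 2 a day to 36. Day 5 is 44 (a fall of 8) and Day 6 is 42 (a fall of 10), so R = 6. Six of 14 values is below 50%, so the AUC is missing. On all days it is 41.0.

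**3. Effect on the Day 14 MMRM difference (simulation, all inputs assumed).** Day 1 mean 50, SD 8; mean fall 9–15, SD 5–8, approached with a time constant of 5 or 10 days; daily noise SD 4; true extra fall on active 3 points; 85 per arm; no drop-out. The fit is by maximum likelihood with unstructured covariance, treatment-by-visit and baseline-by-visit terms. Missingness is monotone, so this equals a sequence of regressions, and Day 29 cannot alter the Day 14 estimate. There were 1,500 runs per setting, with Monte Carlo SE 0.02–0.04.

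| Mean fall / time constant / SD of fall | All days | Cut at R | Kept to R+6 | Loss, cut at R |
|---|---|---|---|---|
| 9 / 10 / 5 | 2.15 | 1.41 | 2.12 | 34% |
| 9 / 10 / 8 | 2.16 | 1.43 | 2.13 | 34% |
| 12 / 10 / 8 | 2.15 | 1.30 | 2.15 | 40% |
| 9 / 5 / 8 | 2.84 | 1.81 | 2.80 | 36% |
| 12 / 5 / 8 | 2.80 | 1.61 | 2.76 | 43% |
| 15 / 5 / 8 | 2.77 | 1.42 | 2.73 | 49% |

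Loss is 1 − (cut at R)/(all days). Across settings 34–72% of placebo and about 50–82% of active patients recover before Day 14. Repeat runs put the top of the cut range at 1.7 to 1.8. With no true effect no bias was found.

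The R+6 column shows the mechanism. Once the seven days that trigger the stop are kept, the stop depends almost wholly on observed values, and the likelihood model recovers nearly the full difference.

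**Minor point, FEV1 AUC.** SAP 7.1.4.5 covers a missing baseline, gaps between two observed values, and fewer than half the values. It has no rule for a missing closing value. If the last value is on Day 10, dividing the observed area by (b − a) gives 9/13 = 69% of a flat FEV1 level; dividing by the observed span gives 100%.

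**The case against.** The strongest reply is that nobody would program the stop. It sits under the event-duration rules, while 8.6.3.7 to 8.6.3.10 name fixed days and 7.1.4.9 calls on Day 15. Using every diary day is the more natural reading. Read strictly, Day R could not be found at all, so the quantified case (compute to R+6, then delete back to R) is a mixture that no passage instructs. This stands in part: the intended analysis is probably the right one. But it departs from a sentence stated twice. The reference in 8.6.3.7 to results that are available would let a programmer who obeys that sentence proceed without noticing the loss.

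Several stronger inferences are not supported:

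- *Most of the effect would vanish.* A comparison restricted to patients who still have a Day 14 value gives only 0.7–1.1 points under the same inputs. The SAP specifies a likelihood MMRM that also uses earlier visits, and its loss is smaller.
- *Endpoint 7 as a whole is compromised.* Its Kaplan–Meier analysis uses first improvement, which occurs on or before Day R, so it is unchanged.
- *False positives in the MMRM.* No bias was found without a true effect.
- *The FEV1 AUC is wrong.* It has a gap with more than one defensible answer. The formula needs the closing value, 8.6.3.4 uses observed cases and 7.2.1 does not impute for drop-outs, all of which favour setting it to missing.

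**Conclusion.** The contradiction follows from the text alone and should be fixed. If the stop is applied, the Day 1–14 EXACT AUC is missing for recovery by Day 6 and lacks a usable closing value for recovery on Days 7–13. These two results need no assumptions beyond the SAP's own rules. The loss of a third to a half of the Day 14 MMRM difference is an illustration. It rests on the assumed score paths and a true 3-point effect, and it arises only if values are cut at Day R.

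The consequences are limited to secondary EXACT analyses. The primary Day 7 FEV1 analysis and the sample size are untouched, and protocol 13.5.1 treats all analyses as exploratory without multiplicity adjustment. The missing FEV1 closing-day rule is a minor clarification.

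**What to change.** 1. In Appendix C, state that the 3-day rolling average is computed on every diary day from Study Day 1 to the end of participation. Use Day R only to derive the event (recovery and duration). The Day 15 value needed in 7.1.4.9 then exists whenever the diary supports it. Changing the AUC divisor alone is not enough: in the first path the observed span still gives 47.5 against 43.1.
2. In SAP 7.1.4.5, state what happens when the 50% rule is met but the closing-day FEV1 is missing: either set the AUC to missing, or integrate to the last observed day and divide by the observed span. Rule out dividing a partial area by (b − a).

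The cost is SAP wording and programming, with no new data. For item 2, setting to missing loses patients. The observed span slightly understates a rising curve: for an assumed rise of 10–30 mL a day to Day 7 and then flat, a curve ending on Day 10 is 6–18 mL low.
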